## Cryptococcal Retention In Care Study (CRICS)

We hypothesize that the prevalence of TmAg in HIV-infected individuals with CD4 counts  $\leq 100$  cells/ $\mu$ L will be at least 5%, and that asymptomatic TmAg is associated with a higher all cause morbidity and mortality.

This study will provide further evidence for the MOH on the potential role of screening for TmAg (and pre-emptive itraconazole therapy for TmAg-positive patients), an approach that may substantially reduce the excess morbidity and mortality in patients starting ART in Tm endemic regions in Asia.

Nearly all patients enrolled in CRICS agreed to the storage of blood specimens for later use; stored samples are identified only by study ID number. All available specimens will be tested for TmAg by ELISA in the OUCRU laboratory in Vietnam. The assay requires 500 mcl plasma out of 500-1000 mcl stored samples.

The study team will match the specimen's ID with the patient's ID as much as possible to ensure that positive TmAg results are returned to the primary doctors who are responsible for the clinical care for the patients. Secondly, doctors in OPCs with positive TmAg patients will be notified about the number of positive tests among their enrolled patients so as to increase their index of suspicion for *T. marneffei* infection. We hope that this will encourage providers to conduct intensive screening for symptoms of Talaromycosis during subsequent patient visits.

Because TmAg is not the nationally approved laboratory test for diagnosis of *T. marneffei* infection in Vietnam, there is no official recommendation for treating asymptomatic patients who are TmAg positive. The decision on antifungal treatment will be made by the primary physicians based on local practice. The treatment regimen for those who are symptomatic will be determined by the primary physician on a case-by-case basis and will follow the standard of care at OPCs in accordance with national guidelines. Per the national guideline the treatment includes amphotericin B (0.7 -1,5 mg/kg/day) for 2 weeks, then itraconazole 200 mg bid (in children 5-6 mg/kg bid) x 8- 10 weeks) or for mild cases or when Amphotericin B is unavailable, itraconazole 200 mg bid x 8 weeks. Maintenance therapy includes itraconazole 200 mg/day in adults and

Funding will be contributed by OUCRU to test specimens for TmAg.

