## Protocol Summary

**Title:** Vietnam Cryptococcal Retention in Care Study (CRICS).

**Purpose:** This is a multicenter prospective cohort evaluation of the implementation of a cryptococcal antigen (CrAg) screening program at selected outpatient HIV clinics (OPCs) and network laboratories in Vietnam. The project will be implemented in 2 phases;

**Phase 1:** From August 2015 to March 2017 [projected], HIV-infected patients who present for HIV care and undergo CD4 testing will be reviewed to determine the proportion of newly presenting patients with advanced disease ( $CD4 \leq 100 \text{ cells}/\mu\text{L}$ ). Reflex CrAg screening will be performed using Lateral Flow Assay (LFA) for those with  $CD4 \leq 100 \text{ cells}/\mu\text{L}$ , per Vietnam national guidelines.

Patients with  $CD4 \leq 100 \text{ cells}/\mu\text{L}$  who present for ART at a study OPCs—CRICS Sites—will be recruited into the longitudinal study and followed up with assessments and the collection of routine and supplemental data for 12 months or through September 2017 (whichever comes sooner). Those who are CrAg-positive, but have no features of central nervous system (CNS) disease, will be treated with high-dose fluconazole. Those with symptoms of CNS disease will be treated according to national guidelines. Survival, retention in care, and other clinical outcomes will be documented for patients who test CrAg-positive and are treated with fluconazole and those who test CrAg-negative. Data from those tested at participating labs but not eligible for enrollment in the longitudinal study will contribute to estimation of the prevalence of CrAg.

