
6. Identify challenges associated with implementation of routine plasma CrAg screening in clinics providing HIV care
	
 
• Percentage of patients with <math>CD4 < 100</math> cells/<math>\mu</math>L who are lost to follow-up or have incomplete documentation
 
• % of patients with no documented clinic visit 30, 60, and 90 days after date of the scheduled clinic appointment
 

7. To disseminate lessons learned with participating sites
	
 
• Reflection and transition workshop
 

8. To estimate the costs of implementing CrAg screening based on data to be collected at 22 participating OPCs participating in Phase 1 and provider costs associated with CM treatment.
	
 
• Total costs and unit cost per person screened, per CrAg+ treated by site, lab facility type, and cost component
 

9. To conduct an incremental cost-effectiveness analysis of CrAg screening compared with a standard of care (no CrAg screening, and treatment for symptomatic CM only).
	
 
• Incremental cost-effectiveness ratio (cost per CM death averted and cost per quality adjusted life year (QALY))
 

10. To project potential cost savings from implementing CrAg screening and financial resources required to implement CrAg screening under different scale-up scenarios and for national rollout.
	
 
• Total cost savings and amount of financial resources required to implement CrAg screening
 

11. To determine the prevalence of Talaromyces marneffei antigenemia (TmAg) in stored CRICS samples using the Mannose phosphate isomerase 1 (MP1) enzyme-linked immunosorbent assay (ELISA)
	
 
• Proportion of stored samples that test positive for TmAg
 

12. To assess the impact of TmAg positivity on mortality
	
 
• Six (6) and twelve (12) month all-causes and TM-related mortality among patients who screen TmAg-positive and TmAg-negative
 

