### **Fluconazole pre-emptive therapy**

4. Current fluconazole dose
5. Timing current symptoms to fluconazole AEs
6. Fluconazole adherence: using self-report questions and visual analog scale

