### **10.3. TmAg in Stored Samples (Sub-study)**

*Talaromyces* (formerly *Penicillium*) *marneffei* is a dimorphic fungus that causes a life-threatening infection in immunocompromised individuals living and traveling in Southeast Asia, China, and India[24, 25]. Talaromycosis is a leading cause of AIDS-related deaths, trailing only TB and cryptococcosis, accounting for 4-15% of AIDS admissions in endemic regions[26-28]. Patients present very late in the course of illness, which has significant treatment morbidity and a mortality rate of up to 30%; treatment options remain limited[26-28]. The recent development of point-of-care cryptococcal LFA (such as CrAg®LFA) has allowed early diagnosis and prevention of CM by pre-emptive fluconazole therapy. The approach is shown to reduce HIV mortality[29], is cost effective in low- and middle-income countries[7, 10]and is in the treatment guidelines in 20 countries.

Stored samples from the CRICS study provides the perfect opportunity to retrospectively investigate the prevalence and clinical significance of TmAg, as the patient population at risk for cryptococcosis is also at risk for talaromycosis.

We will use a novel TmAg detection ELISA developed by the University of Hong Kong for screening[30]. The assay has been validated in the Oxford University Clinical Research Unit (OUCRU) laboratory in Vietnam in more than 600 HIV-infected patients with and without culture-confirmed talaromycosis. The ELISA has the sensitivity and specificity of above 90% and is more sensitive than blood culture in diagnosing talaromycosis (unpublished data). This assay was able to detect TmAg in 9.4% of more than 8,000 archived serum specimens from patients attending HIV clinics in Guangzhou, China[31]. Linked clinical data were not available in that study; therefore the clinical significance of TmAg could not be assessed. Mortality and other clinical outcome data from Phase 1 of the CRICS study will be used to assess clinical significance of antigenemia.

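### Positive TmAg results go back to treating doctors, so objective 12's mortality comparison is at risk of bias for patients whose result is released before follow-up ends; no release date is listed for collection

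*Protocol*

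**What the plan says.** Table 1 of the protocol (Section 2) gives the outcome for objective 12 as "Six (6) and twelve (12) month all-causes and TM-related mortality among patients who screen TmAg-positive and TmAg-negative". Section 10.3 names the data source: "Mortality and other clinical outcome data from Phase 1 of the CRICS study will be used to assess clinical significance of antigenemia". The same section presents the work as an opportunity to "retrospectively investigate the prevalence and clinical significance of TmAg" in stored samples, and as evidence for a possible policy of screening and pre-emptive treatment.

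Section 10.3 then sets out what happens to the results. As far as specimen and patient identifiers can be matched, the team will "ensure that positive TmAg results are returned to the primary doctors who are responsible for the clinical care for the patients". On treatment of asymptomatic positives it says: "The decision on antifungal treatment will be made by the primary physicians based on local practice". Clinics are also told how many of their patients were positive, in the hope that providers will "conduct intensive screening for symptoms of Talaromycosis during subsequent patient visits".

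The Protocol Summary has Phase 1 follow-up last 12 months, cut off at September 2017, and continue while Phase 2 runs. The follow-up variables in Section 10.1.2 cover HIV stage and OIs, symptoms, laboratory tests, ART and fluconazole ("Current fluconazole dose", adherence, adverse effects). They list neither a date of TmAg result release nor any other antifungal. Section 15 routes deaths through SAE review and a cause-of-death form, and describes no classification made without knowledge of TmAg status.

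**The concern.** The objective asks whether TmAg positivity carries excess mortality. If a positive result reaches the doctor while the patient is still in follow-up, the exposure being studied can change that patient's care. Two distortions follow, in opposite directions.

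- **All-cause mortality.** Antifungal treatment prompted by the result would reach positives only. It would lower their later mortality and pull the contrast toward no difference.
- **TM-related mortality.** Whoever reports the cause of death may know the result, so a death in a positive patient is more readily put down to talaromycosis. This pushes the contrast up.

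For affected patients, neither figure would describe the risk of undetected antigenemia, which is what a decision on screening needs. The gap lies in data capture as well as analysis: a later analysis plan can split follow-up at release only if the release date was collected.

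**Working it through.** **The plan's own cohort figure.** Section 6 gives 957 enrolled in about 13 months to 31 October 2016, 74 per month, and a projected follow-up cohort of 1,104.
- To 31 December 2016 (the date in the Table 3 row): 957 + 2 × 957/13 = 1,104.2. This reproduces 1,104.
- To March 2017 (the date in the Section 6 text): 957 + 5 × 74 = 1,327. This does not.

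The main calculation therefore uses accrual to December 2016, with March 2017 as the alternative.

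**Assumptions for the overlap.** Accrual is uniform from 1 October 2015 (month 0) to month 15. Each patient's window runs 12 or 6 months from enrolment. Follow-up stops for all at month 24 (30 September 2017). The release date is not in the readable text and is varied. Timing from ART initiation, as the visit schedule has it, would shift the windows somewhat later.

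**12-month person-time, in units of the monthly accrual rate.**
- Enrolled in months 0–12: 12 × 12 = 144.
- Enrolled in months 12–15, cut at month 24: mean 10.5 × 3 = 31.5.
- Total: 175.5.

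**Part after a release on 1 April 2017 (month 18).**
- Enrolled in months 6–12: 6²/2 = 18.
- Enrolled in months 12–15: 6 × 3 = 18.
- Share: 36/175.5 = 20.5%.

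The 6-month total is 15 × 6 = 90. After month 18 it is 3²/2 = 4.5, or 5%.

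| Release | 12-month window still open, of 1,104 | 12-month person-time after release | 6-month person-time after release |
|---|---|---|---|
| 1 Jan 2017 | 883 (80%) | 67.5/175.5 = 39% | 18/90 = 20% |
| 1 Apr 2017 | 663 (60%) | 36/175.5 = 21% | 4.5/90 = 5% |
| 1 Jul 2017 | 442 (40%) | 13.5/175.5 = 8% | 0% |
| After Sep 2017 | none in follow-up | 0% | 0% |

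If enrolment ran to March 2017, the 12-month shares are 46%, 27%, 11% and 0%.

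**Dilution of the all-cause ratio (illustration).** Observed ratio = true ratio × (1 − share of positives' deaths that would fall after release × uptake × risk reduction). Take a true ratio of 2.0, treatment that halves risk, and deaths spread evenly, so that the person-time share stands in for the share of deaths.
- April release, full uptake: 2.0 × (1 − 0.205 × 0.5) = 1.80.
- April release, 50% uptake: 2.0 × (1 − 0.205 × 0.5 × 0.5) = 1.90.
- April release, enrolment to March 2017, full uptake: 2.0 × (1 − 0.273 × 0.5) = 1.73.
- Release after September 2017: 2.0, no dilution.

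The protocol gives no mortality, uptake or treatment-effect figures, so these inputs are assumptions. The inflation of TM-related mortality cannot be sized from the document.

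**The case against.** The strongest reply is that nothing readable shows the overlap will happen. Section 10.3 calls the work retrospective. Table 9 has a row for TmAg screening, but its cells are lost in the text at hand. The reference to later visits need not mean study visits: these are patients in ongoing HIV care who attend clinic after study follow-up ends. All of this stands, and it makes the point conditional.

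A reader might infer that objective 12 is already biased, or that antifungal treatment after a result goes unrecorded. The document supports neither. Release after September 2017 would leave no affected person-time. The variable list that mentions only fluconazole sits under a fluconazole heading, and treatment data come from chart abstraction. The contents of the Follow-up, Hospitalization and cause-of-death forms are not shown, and inpatient antifungals may be captured there.

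It is also fair that all-cause mortality is immune to attribution bias, that the 6-month outcome is less affected, and that early deaths or low uptake would shrink the dilution. Section 10.3 itself notes that there is no official recommendation to treat asymptomatic positives. Deaths do get study-team review, although Section 15 directs that review at expectedness and relatedness. How to split or censor follow-up can be left to an analysis plan.

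What the reply does not answer is that the protocol plans named return of positives with discretionary treatment, uses the same cohort's mortality as the outcome, and lists no release date among the data to be collected.

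**Conclusion.** The point holds as a conditional risk. For patients whose TmAg result is released before their follow-up ends, the all-cause contrast may be diluted and the TM-related contrast inflated. Because the two act in opposite directions, no single sign can be given for objective 12 as a whole.

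The size depends on the release date. A release between January and July 2017 puts roughly 8% to 39% of 12-month person-time after the result, given uniform accrual to December 2016 and the September 2017 cut-off. The April 2017 illustration moves a ratio of 2.0 to about 1.8 only with full uptake, halved risk and evenly spread deaths. This is a cheap improvement worth making, and it is no argument against returning results.

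**What to change.** Keep the return of results and leave clinical management unchanged. Then:

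1. Record the calendar date on which TmAg results were released to each OPC.
2. Record any systemic antifungal other than fluconazole, with start and stop dates, unless the existing forms already do so.
3. In the main objective 12 analysis, use time-to-event methods and censor TmAg-positive and TmAg-negative patients of an OPC at that OPC's release date. The same calendar rule for both groups avoids shortening follow-up in positives alone. It also covers positives whose identifiers could not be matched, since the clinic is told its count of positives. Report full follow-up as a sensitivity analysis.
4. Have the existing study-team review classify TM-related death without the TmAg result.

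The cost is one date per OPC, at most one added form line, and some analysis and review wording. The statistical price is fewer deaths and a somewhat wider interval in the main analysis. If results are released only after follow-up has ended, the censoring rule changes nothing.

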### **10.4. Data storage**

CRFs will be used as a data collection tools. Source documents which are generated during the study by the clinical staff will be kept at the study sites. CRFs and other project documents

## Cryptococcal Retention In Care Study (CRICS)

will be stored in a restricted-access room that only investigators and study staff can access. At NHTD, all project documents and copies of CRFs will also be protected in a secure room or locked cabinet; and personal data existing in non-digital format including CRFs or signed consent forms, containing names, addresses and signatures will be stored separately from data in a separated locked cabinet. After completion of the study, all study documents kept at study sites will be transferred back to NHTD. All essential documentation for all study patients will be maintained in original paper format by the investigators in a secured storage facility for a minimum of 3 years and as required by local regulations thereafter. All stored records will be kept secure and confidential.

### **10.5. Data transfer**

Every 1-2 months, original completed CRFs from nearby study sites will be securely transported to NHTD for data entry and returned to the site afterwards for storage. CRFs from remote sites will be photocopied by the OPC POC and sent to NHTD for data entry. The original CRF will be maintained at the OPC. The copies of CRF or original CRFs will be secured in a locked box and protected by study staff during transferring.

Following data entry, data will be stored in a personal computer (PC) secured with a password. A data entry officer will be responsible for data entry into the PC, using data entry software. The PC will have firewall protection and security-related upgrades and patches to operating systems to avoid viruses and malicious code. Only designated NHTD staff will be approved for access to the PC containing study data. It's required to encrypt data containing personal information before they are stored. Confidential data such as those containing personal information will not be stored on servers or computers connected to an external network, particularly servers that host Internet services. Sending personal or confidential data via email or other file transfer means without encrypting is also not allowed.

Besides, to reduce risk as far as possible, backups will be made after every change to data. There are at least two different forms of storage, for example on hard drive and on CD in case of accidental loss of data. Data files will be kept in portable computers, non-network computers and home-based computers.

## **10.6 Data ownership, governance, sharing, dissemination**

The database and samples arising from this study will remain the property of NHTD and investigators. NHTD also carries responsibilities to protect confidentiality and the privacy of research participants. Access to certain data sets will therefore be carefully managed and granted in a transparent manner to all appropriately qualified researchers. The final study database will be made available to and will be archived at NHTD. Investigators not affiliated with this study who are interested in analyzing the study data, will submit a brief proposal that will be reviewed by a study team that includes at least one study investigator from NHTD and one from CDC.

In terms of TmAg sub-study, all TmAg-related data will reside at NHTD but will also be accessible all co-investigators from NHTD, CDC and OCRU.

## **10.7 Data quality assurance**

Before sending to NHTD, the OPC POC will check the quality of all CRFs to ensure that all information has been properly collected and recorded. Data will be entered in an MS Access database. The MS Access sets up the tables before you can enter data and the data entry forms are incredibly flexible. There are different objects within the Access database file such as tables (which store the data), queries (which ask questions of the data), forms (used for data entry and editing) and reports (for summarizing data) – but there is just one single file (with the extension .mdb) so only one file to backup and/or pass to colleagues. Double data entry will be used to eliminate mistakes during data entry by checking for agreement with computer verification. The data manager at NHTD will provide feedback via phone calls and through coordinator's visits to the study sites regarding any errors or missing data on a monthly basis, but forms are only transferred to NHTD every 2 months. During data processing, the information will be checked again for completeness and consistency.

# **11. Data Analysis**

## **Data analysis plan:**

### **Primary objectives:**

Proportions will be calculated and presented with associated 95% confidence interval (CI). Clustering effect will be taken into account when calculating 95% CI.

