**Objectives:**

**Primary objectives:**

- To estimate the proportion of people living with HIV (PLHIV) who have advanced disease ( $CD4 \leq 100$  cells/ $\mu L$ ) at presentation to HIV care;
- To determine the prevalence of CrAg-positivity among HIV infected patients with  $CD4 \leq 100$  cells/ $\mu L$  newly enrolled in care in Vietnam;
- To determine clinical outcomes including common causes of mortality for PLHIV with  $CD4 \leq 100$  cells/ $\mu L$  who are enrolled in a programmatic rollout of screening for CrAg;
- To estimate the 12-month mortality among two groups of HIV-infected patients with  $CD4 \leq 100$  cells/ $\mu L$  who are newly enrolled in care and treatment:
  - Those who are CrAg-positive and are treated with high-dose fluconazole
  - Those who are CrAg-negative

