## 2. Study Objectives and Outcome Measures

**Table 1. Study objectives and outcome measures**

Primary objectives	Outcome measures
1. To estimate the proportion of people living with HIV (PLHIV) who have advanced disease ( $CD4 \leq 100 \text{ cells}/\mu\text{L}$ ) at presentation to HIV care	
 
Proportion of HIV-infected adults who have <math>CD4 \leq 100 \text{ cells}/\mu\text{L}</math>
 

2. To determine the prevalence of CrAg-positivity among HIV-infected patients with $CD4 \leq 100 \text{ cells}/\mu\text{L}$	
 
Proportion of patients who are CrAg-positive among all HIV-infected adults who have <math>CD4 \leq 100 \text{ cells}/\mu\text{L}</math>
 

3. To determine clinical outcomes including common causes of mortality for PLHIV with $CD4 \leq 100 \text{ cells}/\mu\text{L}$ who are enrolled in a programmatic rollout of screening for CrAg	
 
Reported causes of death
 
Proportion of patients with HIV-related hospitalizations at 6 and 12 months
 
Proportion of patients with new AIDS-defining OIs/conditions at 6 and 12 months
 

4. To estimate the 12-month mortality among two groups of HIV-infected patients with $CD4 \leq 100 \text{ cells}/\mu\text{L}$ who are enrolled in care and treatment: 
 
Those who are CrAg-positive and are treated with high-dose fluconazole;
 
Those who are CrAg-negative.
 
	
 
Twelve (12) month all-causes and CM-related mortality among patients who screen CrAg-positive and CrAg-negative
 

Secondary objectives	Outcome measures

5. To estimate the 12-month retention in care among two groups of HIV-infected patients with <math>CD4 \leq 100</math> cells/<math>\mu</math>L who are newly enrolled in care and treatment:
 
 
• Those who are CrAg-positive and are treated with high-dose fluconazole
 
• Those who are CrAg-negative
 
	
 
• Twelve (12) month retention among patients who screen CrAg-positive and CrAg-negative
 

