### **3. Study design and use LFA in study and non-study sites**

This is multicenter, prospective, cohort evaluation of a CrAg screening program among HIV-infected patients with  $CD4 \leq 100$  cells/ $\mu L$  who are newly enrolled in care at selected HIV OPCs in Vietnam, conducted in collaboration with the Vietnam Administration for HIV/AIDS Control (VAAC). The evaluation will be implemented in 2 phases.

Phase 1: Enrollment in the longitudinal study will take place from August 2015-March 2017 [projected approval of the protocol amendment for Phase 2]. In Phase 1, patients with  $CD4 \leq 100$  cells/ $\mu L$  who are newly presenting for HIV care at 22 outpatient sites in the North, Middle, and South of Vietnam have been screened for cryptococcal disease by testing their plasma for CrAg using LFA and enrolled into the study for 12 months' follow-up.

Phase 2 will start in April 2017 or when the protocol amendment is approved and will continue for up to 3-6 months. After 3-6 months, transition of the program will be discussed with VAAC for continued programmatic rollout. . During this phase we will perform a cost and cost-effectiveness analysis of CrAg screening and continue CrAg screening as a routine service without enrollment in prospective follow up. CrAg tests will be made available to screen patients with  $CD4 \leq 100$  cells/ $\mu L$  including those who are treatment experienced in selected existing and additional sites, and to screen hospitalized patients with  $CD4 \leq 100$  cells/ $\mu L$  and/or suspected CNS infections in hospitals affiliated with the CRICS OPCs. CrAg testing will also be used for diagnostic purposes among patients with symptoms or signs of meningitis. We will monitor the prevalence during Phase 2 but screened patients will not be followed up prospectively in the study. As CrAg screening is a WHO and Vietnam MOH national recommendation, it is considered SOC for persons with advanced HIV ( $CD4 \leq 100$  cells/ $\mu L$ ), and reflexive testing does not require informed consent. Testing will be expanded during Phase 2 to screen other patients at selected Phase 1 and additional sites without enrolling them into follow up.

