### **Enrollment in the follow-up study**

In Phase 1, enrollment in the longitudinal cohort will be offered to eligible patients who have  $CD4 \leq 100$  cells/ $\mu L$  enrolled at and plan to receive ongoing outpatient care at one of the selected study OPCs (Table 2). Those who test plasma CrAg-positive and have no symptoms of meningitis will be treated with high-dose fluconazole. Study participants will be followed from the time of plasma CrAg screening for a minimum of 6 months and up to 12 months depending upon when they are recruited with respect to the study expected duration. Routine clinical data will be abstracted from medical records and supplemental data will be collected to determine treatment outcomes and related factors. Fluconazole will be provided by the study for patients enrolled in the follow-up program during Phase 1 for the duration of the study. For those who tested CrAg-positive and are still receiving maintenance fluconazole at the end of their longitudinal follow up, fluconazole will be provided through routine sources.

In Phase 2, screened patients will not be followed up prospectively. However, fluconazole supply for identified CrAg-positive patients will be provided by the project if patients do not otherwise have access through their OPCs.

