## 6. Sample size calculation:

The two primary outcomes of the study are 1) the estimate of the percentage of prescreened patients who have  $CD4 \leq 100$  cells/ $\mu L$  and 2) Of those with  $CD4 \leq 100$  cells/ $\mu L$ , the estimate of the percentage who are CrAg+. For these primary outcomes, data will come from both Phase 1 and Phase 2. From study initiation to October 31 2016 (approximately 13 months), we prescreened 2,612 participants, and 1068 of these had a  $CD4 \leq 100$  cells/ $\mu L$ . Of those, 957 enrolled, and 25(2.6%) were CrAg+. Assuming a similar enrollment rate (74 per month), upon the completion of Phase 1 (March 2017), we will have prescreened 3,014 participants and would expect 1,232 to have  $CD4 \leq 100$  cells/ $\mu L$  and 1,104 to be enrolled in the follow up study. Of these, we would expect approximately 29 to be CrAg+.

For Phase 2 (presumably from February 2017 to September 2017), plan to prescreen an additional 1,808 patients. Taking both data from Phase 1 and Phase 2 into account, we would expect to prescreen 4,822 patients and to document 1,972 patients with  $CD4 \leq 100$  cells/ $\mu L$ . In total, we would expect approximately 46 patients to be CrAg+.

Table 3 presents confidence limits for the two primary outcomes based on these assumptions and incorporating a design effect (DEFF) to account for the within-facility clustering of observations. The design effect is computed as  $[1+(m-1) \text{ ICC}]$  where  $m$  is the average number of patients per facility and ICC is the intraclass correlation coefficient. There is no local data on which to base assumptions about the magnitude of the within-clinic correlation in Vietnam, but a recent publication reports intraclass correlation coefficients (ICCs) of about .02 or smaller for health-related variables in an HIV-positive clinic population in sub-Saharan Africa [4]. Taking data from Phase 1 into account only, for the first primary outcome,  $m$  is 137 (3014/22) and for the second primary outcome,  $m$  is 56 (1,232/22). Taking data from both Phase 1 and Phase 2 into account,  $m$  is 219 (4822/22) and is 90 (1972/22) for the first and the second primary outcomes respectively.

**Table 3. Precision for primary study outcomes based on projected enrollment in Phase 1 (through March 2017) and Phase 1 + Phase 2 (projected through September 2017)**

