Pre-screened	% with CD4≤100	Design Effect	95% confidence limits	Number tested for CrAg	% CrAg-positive	Number CrAg+	Design Effect	95% confidence limits
Phase 1 (projected through Dec 31, 2016)								
3,014	40.9	3.72	37.5, 44.3	1,232	2.6	29	2.10	1.30, 3.90
Phase 1 + Phase 2 (projected through September 2017 among 22 study OPCs only)								
4,822	40.9	5.36	37.7, 44.1	1,972	2.6	46	2.78	1.40, 3.80

Note: Confidence limits are inflated by a design effect of  $[1+(m-1) \rho]$  where m is the average number of patients per facility and  $\rho$  is the intraclass correlation coefficient.

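### 12-month mortality is listed as primary, but Section 11 gives only a proportion for it, and about 20% to 33% of the cohort cannot reach 12 months from enrollment

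*Protocol*

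**What the plan says.** **Objective.** The primary objectives in the Protocol Summary include "To estimate the 12-month mortality among two groups of HIV-infected patients with" CD4 of 100 or below, split by CrAg result. The measure in Table 1 (Section 2) is "Twelve (12) month all-causes and CM-related mortality among patients who screen CrAg-positive and CrAg-negative". Section 6, however, names only two primary outcomes, the share with low CD4 and the share CrAg-positive. Mortality is not one of them.

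**Method.** Under primary objectives, Section 11 says "Proportions will be calculated and presented with associated 95% confidence interval (CI" and that the interval will allow for clustering. Nothing else stands under that heading. Logistic regression for factors linked to death, and proportional hazards for time to death (including a comparison with a historical cohort), stand under secondary objectives.

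**Length of follow-up.** The Protocol Summary has patients followed "for 12 months or through September 2017 (whichever comes sooner". Section 3 says "Study participants will be followed from the time of plasma CrAg screening for a minimum of 6 months and up to 12 months". Section 10 (Overview) starts follow-up at enrollment and lets it run up to 12 months after ART initiation. Section 7.7 and Table 4 tie the 12-month visit and the off-study form to ART initiation.

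**Accrual.** Section 3 says "Enrollment in the longitudinal study will take place from August 2015-March 2017". Section 6 expects "1,104 to be enrolled in the follow up study" at completion of Phase 1 in March 2017. Table 3 labels the same projection "Phase 1 (projected through Dec 31, 2016".

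**The concern.** A simple proportion needs every patient in the denominator to have a known status at the time point. CD4 category and CrAg result meet that condition. Death by 12 months does not, because patients who enroll after September 2016 reach the September 2017 cut-off before month 12.

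The analyst would then have to choose a denominator. Counting all enrolled treats unobserved months as survival. Keeping deaths and completers only removes living patients but not dead ones. Restricting to patients enrolled by 30 September 2016 avoids the truncation but discards the later part of the cohort. The protocol does not say which applies, so the choice could be made after the deaths are known. The unsettled starting point adds a smaller ambiguity.

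**Working it through.** **Inputs.** Section 6: 957 enrolled by 31 October 2016 over about 13 months; 74 per month; 1,104 projected; 22 clinics; ICC 0.02; about 29 CrAg-positive. Protocol Summary: cut-off September 2017, taken here as 30 September. Assumptions: a 12-month risk of 15%, uniform accrual, and a hazard that is constant or falling (Weibull shape 1 or 0.5).

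**1. The protocol's 1,104.** 957/13 = 73.6 per month. Two more months give 957 + 2 × 73.6 = 1,104, so the figure corresponds to the end of December 2016. Five more months, to March 2017, give 957 + 5 × 73.6 = 1,325.

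**2. Share without a possible 12-month status**, i.e. enrolled after 30 September 2016:

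| Start of the 12 months | Accrual to Dec 2016 | Accrual to March 2017 (assumed to continue) |
|---|---|---|
| Enrollment | 3 × 73.6 = 221; 221/1,104 = 20.0% | 6 × 73.6 = 442; 442/1,325 = 33.3% |
| Screening, two weeks earlier (assumed) | 2.5 × 74 = 185; 185/1,105 = 16.7% | 5.5 × 74 = 407; 407/1,327 = 30.7% |

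If the 957 had accrued over the 15 months from August 2015 (63.8 per month), the enrollment row would be 191/1,085 = 17.6% and 383/1,276 = 30.0%.

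**3. Effect of the denominator at a true risk of 15%.** Let D be the share of enrolled patients seen to die within 12 months and before the cut-off, and c the share who could be followed for 12 months. The all-enrolled proportion is D. Deaths plus completers gives D/(D + 0.85c).

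December, constant hazard: those truncated have 9 to 12 months of follow-up and an average risk of 13.25%. So D = 0.8 × 0.15 + 0.2 × 0.1325 = 0.1465, and 0.1465/(0.1465 + 0.8 × 0.85) = 17.7%.

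March, falling hazard: D = 0.1435, and 0.1435/(0.1435 + 0.6667 × 0.85) = 20.2%.

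| Denominator | Dec 2016 | March 2017 | Error in points |
|---|---|---|---|
| All enrolled | 14.6–14.8% | 13.8–14.4% | 0.2 to 1.2 too low |
| Deaths plus completers | 17.7–17.9% | 19.6–20.2% | 2.7 to 5.2 too high |

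These figures reflect truncation alone, with no loss to follow-up.

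**4. Comparison with sampling error.** CrAg-negative: n = 1,104 − 29 = 1,075; m = 1,075/22 = 48.9; DEFF = 1 + 47.9 × 0.02 = 1.96. Half-width = 1.96 × √(0.15 × 0.85 × 1.96/1,075) = 3.0 points. CrAg-positive: 1.96 × √(0.15 × 0.85/29) = 13.0 points. With 4 deaths in 29 the exact 95% interval is 3.9% to 31.7%. The protocol states neither half-width.

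**The case against.** The strongest reply is that this is detail for the analysis plan. Section 11 does not say that the proportion is crude. A Kaplan-Meier 12-month risk is itself an estimated proportion with a confidence interval, so the sentence does not exclude it. Section 6 names the two prevalence outcomes as primary, and the sentence fits those. Mortality methods, including proportional hazards, appear a paragraph later. On this reading the fault is mainly one of placement under headings.

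Part of this stands. The wording permits a better estimator, and time-to-death analysis is planned. But the Protocol Summary and Table 1 both call mortality primary, and the one method stated for primary objectives is unsuitable for it when taken at face value. A proportional hazards model does not by itself give a 12-month risk in each group.

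Two stronger readings are tempting and are not supported:

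- A reader might infer that reported mortality could lie anywhere from 13.8% to 20.2%. The upper end needs living patients with short follow-up to be dropped. The protocol leaves that open but nowhere proposes it.
- A reader might take every mention of the ART-initiation clock as a contradiction. Under Definition of end points (Section 3), loss to follow-up is deliberately described from both enrollment and ART initiation. The ART-based dates in Section 7.7, Table 4 and Section 10 schedule visits and forms and do not define an analysis origin. Moving the origin from enrollment to screening one to three weeks earlier changes an assumed 15% risk by only 0.1 to 0.8 points.

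**Conclusion.** The point holds as a should-fix of moderate size. An outcome listed as primary has a stated method that fits the prevalence outcomes but not a 12-month risk in a cohort with truncated follow-up. The 20% rests on the protocol's own 1,104 with enrollment as the start. The 33% also assumes that accrual continues at about 74 per month to March 2017. From screening two weeks earlier, the range is about 17% to 31%.

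With all enrolled patients as denominator, the error is below the half-width in CrAg-negative patients. With deaths plus completers, it is about equal to or larger than that half-width. For the CrAg-positive group the choice matters much less than having only about 29 patients. The error sizes depend on the assumed 15% risk.

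**What to change.** - **Estimator.** In Section 11, estimate 12-month all-cause mortality in each CrAg group by Kaplan-Meier, censoring at last contact or at the September 2017 administrative end, with a cluster-adjusted 95% interval. Estimate CM-related death by cumulative incidence, with other death as a competing event. State that the interval for CrAg-positive patients will be wide and its cluster adjustment unstable.
- **Time zero.** Use enrollment (consent, which Section 13.1 requires to be dated) for mortality. Reconcile Section 3 (Enrollment in the follow-up study), Section 7.7, Table 4 and Section 10 (Overview) with it. The ART-initiation clock can stay for the retention and loss indicators.
- **Status of the outcome.** Make the Protocol Summary, Table 1 and Section 6 agree on whether mortality is primary.
- **Optional.** Add a sensitivity analysis for loss that is related to the risk of death.

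The cost is low, with no new patients or visits. The planned time-to-death analysis already needs dates of death; confirm that the off-study form and Appendix 10B record them. One small downside remains: patients who never start ART, or who were already on it at entry, may have no ART-based visit at 12 months from enrollment. Their vital status must come from clinic records, or they are censored at last contact.
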